The doses to be tested for famotidine are 20 mg thrice daily, 40 mg thrice daily, 80 mg thrice daily and no famotidine. The doses to be tested for n-acetyl cysteine are 600 mg thrice daily, 1200 mg thrice daily and 1800 mg thrice daily. The dose combinations are labelled 1 through 12 and are zoned as illustrated in Figure 10. The first zone has the combination of the lowest dose of each drug. The second zone has the combination of the lowest dose of each drug with the middle dose of each drug. The dose escalation starts with the first zone and follows with the second zone and then each combination of doses in the zone next closest to the coordinate

[figure not shown]

Figure 10. Dose Combinations of N-Acetyl Cysteine and Famotidine

origin shown in figure 10. Combination doses in the same zone are tested simultaneously using block randomization to control the number of patients for each open dose. Some combinations doses may close, in which case blocked randomization is applied to the remaining open combination doses in the same zone. A modified “3+3” design¹⁷² will be used for the initial dose escalation.

To find acceptable dose levels any grade 3 or higher toxicity will be considered a dose-limiting toxicity (DLT). The modified “3+3” design proceeds as described below. Three patients receive dose level 1. Their responses determine the subsequent steps as described in the following decision rules.

- (1) If two patients (2/3) experience DLT, then we close dose level 1 and all larger doses to testing.
- (2) If no patient experiences DLT, then we designate dose level 1 as an admissible dose, and open doses in zone 2 for testing.
- (3) If only one of the first three patients (1/3) experiences DLT, then we assign three more patients to dose level 1. In this case, we assign up to six patients to this dose, and the following decision rules apply:
 - a. If only one of the six patients (1/6) experiences DLT, then we designate dose level 1 as an admissible dose, and open doses in zone 2 for testing.
 - b. If two of the six patients (2/6) experience DLT, then we designate dose level 1 as an admissible dose, and doses in zone 2 and higher are closed to testing.
 - c. If more than two of the six patients (>2/6) experience DLT, then we close dose level 1 to testing, and we also close doses in zone 2 and higher.

ii) Study Procedure

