Data will primarily be abstracted via chart review and patient's history and physical exam and by patient completed medication logs and daily diary of temperature and symptoms. Data of Oxygen saturation level and vital signs will also be obtained directly from the subjects Vivify® device.

V) ADEQUACY OF PROTECTION AGAINST RISKS

i) Recruitment and Informed Consent

See attached Informed Consent Form.

ii) Protection against Risk

[name]., will serve as the medical monitor and will chair an internal Data and Safety Monitoring Board to ensure the safety of all subjects and their data.

It is essential that all AEs, including serious adverse events (SAEs), which occur during the course of research subjects' involvement in a study are appropriately identified, documented, reported, and managed in order to ensure the subjects' continuing safety. This is the responsibility of the investigative site.

The PI will Complete in REDCap® an NCI Adverse Event Serious Adverse Event CTCAE v5 form within 24 hours of notification of an adverse event by a subject, research assistant, co-investigator, outside provider or by any other means in which this information may be obtained. If the event is life-threatening or fatal, this form will be completed immediately, and the event will be reported immediately to [name] and the IRB. Whenever this form is completed by the PI, an email will be immediately sent [name] and any other individuals specified by [name]. Whenever this form is completed by the PI and a Serious Adverse Event has occurred, an email will be immediately sent via the REDCap® alert mechanism to the IRB Chair and any other individuals specified by the IRB. This copy of this form can be found in the Appendix and includes all the elements described below.

Adverse Event (AE)

An AE in this clinical trial is defined as any unfavorable change in a research subject that may occur during or after administration of the investigational drugs. There need be no causal relationship to the investigational drugs and may be due to the SARS-CoV-2 infection or for any other reason. This change does not have to be caused by the investigational product or study procedures to be described as an AE.

AEs may include:

- Physical signs or symptoms
- Abnormal laboratory values

- Changes in vital signs, physical examinations or an electrocardiogram (ECG)
- An increase in the frequency or intensity (worsening) of symptoms that were present before study enrolment

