Probable (must have three [3])	
 1. Has a reasonable temporal relationship to the investigational drugs 2. Could not have readily been produced by the subject's clinical state or have been due to environmental or other interventions 3. Follows a known pattern of response to the investigational drugs 4. Disappears or decreases with reduction in dose or cessation of study drugs and recurs with re-exposure
Possible (must have two [2])	
 1. Has a reasonable temporal relationship to the investigational drugs 2. Could not have readily been produced by the subject's clinical state or have been due to environmental or other interventions 3. Follows a known pattern of response to the investigational drugs 4. Disappears or decreases with reduction in dose or cessation of study drugs and recurs with re-exposure
Unlikely (must	
 1. Does not have a temporal relationship to the investigational drugs

have two [2])	
 2. Could readily have been produced by the subject's clinical state 3. Could have been due to environmental or other interventions 4. Does not follow a known pattern of response to the investigational drugs 5. Does not reappear or worsen with reintroduction of investigational drugs
--------------------------	---

Duration of AEs

Another important element for evaluation of an AE is the duration of the event. Onset of the event will be measured from the onset of signs and symptoms. Resolution of the event will be recorded as well, which we will define as the point when all signs and symptoms have subsided.

Some events continue or change in severity over time. Capturing this information is also important. Changes in severity such as when an event improves from severe to mild will be recorded as separate events, with separate intensities and durations collected. The ongoing nature of the event will be noted in the subject's research record.

Determining Severity

An important component in evaluating AEs is their severity. Severity refers to the intensity of the event and will be indicated as mild, moderate, or severe, as shown in the table below.

Grading of Severity of AEs Based on Signs and Symptoms	
None	No signs/symptoms or within normal limits
Mild	Minor signs/symptoms; no specific medical intervention required; asymptomatic laboratory findings only, radiographic findings only; marginal clinical relevance

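### The adverse-event resolution rule has no return-to-baseline option, so the duration of a worsened COVID-19 symptom runs to the end of the illness; the onset rule also leaves room for a pre-dose date

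*Combined protocol and SAP*

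**What the plan says.** All the relevant text is in the protocol, section V) ii) Protection against Risk, unless stated otherwise.

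- **Definition.** Under Adverse Event (AE), an AE is "any unfavorable change in a research subject that may occur during or after administration of the investigational drugs", with no causal link required. The listed examples include "An increase in the frequency or intensity (worsening) of symptoms that were present before study enrolment".
- **Onset.** Under Duration of AEs: "Onset of the event will be measured from the onset of signs and symptoms".
- **Resolution.** The same paragraph requires resolution to be recorded, "which we will define as the point when all signs and symptoms have subsided".
- **Severity changes.** The next paragraph says that changes in severity "will be recorded as separate events, with separate intensities and durations collected". Its only example is an improvement.
- **Causality.** In the causality table, a reasonable temporal relationship is the first of four criteria for relatedness. The Unlikely category needs two of five criteria, which include "Does not have a temporal relationship to the investigational drugs" and "Could readily have been produced by the subject's clinical state".
- **Population.** Under III) ii) Study Procedure, only subjects who test positive for SARS-CoV-2 are randomized and dosed.

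**The concern.** The AE definition makes the event the change from the earlier state. The duration rules refer only to the symptoms and never to that earlier state. For a symptom that the subject already had, these are different things.

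The situation should be common. Subjects are recruited in the emergency department, and section III) vi) expects that they may be more symptomatic than other infected people. The drug-reaction lists (Side effect profile of NAC, Side effect profile of FAM, and section IV) i)) and the telehealth tip sheet for COVID-19 patients share nausea, vomiting, diarrhea, dizziness, fever and breathing difficulty.

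Safety and toxicity is the primary outcome, and the protocol calls duration an important element in evaluating an AE. At stake is whether recorded durations describe the drugs or the infection, and whether two investigators would date the same event alike.

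**Working it through.** The plan gives no figure to reproduce. The check sets the rules side by side and then counts criteria in the causality table.

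**1. Resolution.** Take one symptom with dates *a* (symptom starts), *d* (first dose), *w* (worsens on drug), *b* (back to its pre-dose level) and *c* (gone), in the order a < d < w < b < c. By the AE definition the event is the worsening, so its duration is b − w.

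- *Worsening within one severity category.* The severity-change rule does not apply. The event closes at *c*, so its duration is c − w even when onset is correctly placed at *w*. Excess: (c − w) − (b − w) = c − b.
- *Worsening across a severity category.* The step down at *b* is a change in severity. The first event closes at *b*, and a second, lower-grade event opens at *b* and stays open to *c*. That gives two records instead of one, with total open time c − w. The second record describes a symptom at its pre-dose level, which is not an unfavorable change.

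In both cases c − b is illness time. Study Procedure lets dosing end once symptoms have improved (with its other conditions met) and does not require them to be gone, so *c* can fall after the last dose.

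**2. Onset.** If onset is read as the start of the symptom, the date is *a*, before *d*. In the first case above the excess becomes (c − a) − (b − w) = (c − b) + (w − a). This reading contradicts a definition confined to changes during or after administration. If onset is read as the start of the change, the date is *w*. The text does not say which is meant.

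**3. Possible effect on causality.** Take a symptom that the infection could explain, with no environmental cause. Let T = temporal relationship, P = known pattern of response, D = improves on stopping and recurs on re-exposure, and R = the Unlikely criterion on not reappearing with reintroduction (each 1 if met, 0 if not). Then:

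- related criteria met = T + P + D (the clinical-state criterion fails);
- Unlikely criteria met = (1 − T) + 1 + (1 − P) + R.

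P, D and R give 2 × 2 × 2 = 8 combinations. D and R cannot both hold, which removes 2 and leaves 6. Entries show related / Unlikely counts. Where more than one related category is met, only the highest is shown.

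| P | D | R | Pre-dose onset (T = 0) | Onset at worsening (T = 1) |
|---|---|---|---|---|
| 0 | 0 | 0 | 0 / 3: Unlikely | 1 / 2: Unlikely |
| 0 | 0 | 1 | 0 / 4: Unlikely | 1 / 3: Unlikely |
| 0 | 1 | 0 | 1 / 3: Unlikely | 2 / 2: Possible and Unlikely |
| 1 | 0 | 0 | 1 / 2: Unlikely | 2 / 1: Possible |
| 1 | 0 | 1 | 1 / 3: Unlikely | 2 / 2: Possible and Unlikely |
| 1 | 1 | 0 | 2 / 2: Possible and Unlikely | 3 / 1: Probable |

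With a pre-dose date, Unlikely is met in 6 of 6 combinations and is the only category met in 5. With the date at worsening, 4 of 6 reach Possible or higher and 2 stay Unlikely. The plainest case, a known drug effect with no re-exposure (fourth row), moves from Unlikely to Possible. So the date can matter, but it does not settle the category alone.

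**The case against.** The strongest reply is that the onset sentence dates the event, and the event is already defined as a change during or after dosing. On that view onset is the onset of the increase and no pre-dose date arises. This is the more coherent reading. It shows that the onset sentence is ambiguous and does not direct investigators to a pre-dose date. It does nothing for resolution, where the wording is explicit.

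A second reply is that the severity-change rule gives a step up to severe its own dates. It can, although its application to a first worsening over an unrecorded pre-dose symptom is not spelled out. Two gaps remain: worsening within one category, and the last mild episode, which does not close at the pre-dose level.

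Third, the duration paragraph is not tied to the causality table. Causality is described as a medical judgement, and the Sponsor-Investigator and the Data and Safety Monitoring Board review each determination. That stands, so a reader who infers that these events must be scored Unlikely goes too far.

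A reader might also infer that real toxicity is lost from the safety result or from the escalation decisions. The documents do not support this. AEs are recorded whatever their cause, so the event stays in the data. The DLT rule under III) i) covers toxicity of grade 3 or higher and names no relatedness category. It can be argued that the word toxicity implies attribution, but the plan does not say so.

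Finally, laboratory findings have no symptom onset. This point is weak: the severity table, headed as based on signs and symptoms, itself includes asymptomatic laboratory findings, so the phrase may be meant broadly. A specimen date would settle it.

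**Conclusion.** The point holds for resolution and, as an ambiguity, for onset. Followed literally, the resolution rule overstates the duration of a worsened baseline symptom by c − b. When a severity category is crossed, it also adds one AE record for a symptom that is back at its pre-dose level. The size in days cannot be given because the documents contain no symptom durations. The plan also names no specific analysis of AE duration, so the direct damage is to the descriptive safety data.

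A pre-dose onset is one possible reading, at odds with the AE definition. If it were used for the timing criterion it could change the causality category, as the six combinations show for a symptom that the infection could explain. That part assumes the literal reading and assumes that the recorded onset date feeds the causality table; neither is stated. An effect on DLT counting or dose escalation is not shown. The AE form's own date fields could not be checked from the text available.

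**What to change.** Change three sentences under Duration of AEs:

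- **Onset:** the date a sign or symptom first appears after the first dose, or first exceeds its recorded pre-dose level. For laboratory findings, the specimen date.
- **Resolution:** disappearance, or return to the pre-dose level.
- **Severity changes:** a return to the pre-dose level closes the event and opens no new mild one. Without this amendment the severity-change sentence would contradict the new resolution rule.

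Use the enrollment CAP-SYM 18 and history as the baseline. Add one diary entry before the first dose for symptoms that these do not cover, because the CAP-SYM 18 items are not shown and its coverage of nausea or diarrhea cannot be confirmed. Subjects already receive diary forms at enrollment.

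The cost is protocol wording, matching help text on the AE form and one extra diary entry. The small downside is that staff must check the baseline when dating an event.

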Assessment	Enrollment (within 24 hours of a SARS CoV-2 Test)	Weekly after Randomization Until Hospital Admission or Study Completion	Upon Study Completion (If SARS CoV-2 Positive)	If Hospitalized and Until Discharge
Informed Consent	X			
Urine Pregnancy Test (If appropriate)	X			
Blood Type and Rh	X			
(Serum) Cytokines (IL-1 β , IL-2, IL-6, IL-8, IL-10, IFN γ , TNF α and GM-CSF), Tryptase and Glutathione Level	X		X	X (once upon hospitalization)
(Urine) F2-Isoprostane/Creatinine Ratio, TMRSS2 Cytokines (IL-1 β , IL-2, IL-6, IL-8, IL-10, IFN γ , TNF α and GM-CSF) and N-methylhistamine	X	X	X	X (once upon hospitalization)
CURB-65 Score	X			
CAP-Sym 18	X			
IPSS (men only)	X			
Weekly Review of Daily Medication Logs and Daily Diary		X		
Weekly Assessment CRFs		X		
Completion Data CRF				
Hospital Tracking CRFs				
			X	X

Medication Log Form

Medication Log Form: Trial of FAM and NAC for SARS-CoV-2							
Subject Study Number: _____				Week #: _____			
Day of Week Trial Started: _____ (fill this in by hand under Day 1 below)							
Dose of Famotidine 20 mg tablets Assigned to Taken Thrice Daily: 0 1 2 3 (Research Staff to Circle)							
Number of N-Acetyl Cysteine Capsules Assigned to Take Thrice Daily: 1 2 3 (Research Staff to Circle)							
	Day 1	Day 2	Day 3	Day 4	Day 5	Day 6	Day 7
Day of Week							
Date (MM/DD)							
Famotidine (20 mg tablet)							
1 st Dose							
2 nd Dose							
3 rd Dose							
N-Acetyl Cysteine (600 mg capsule)							
1 st Dose							
2 nd Dose							
3 rd Dose							

Instructions for Research Staff:

1. Print a minimum of 4 Sheets and enter Subject Study Number on each. Write in week numbers 1 to 4 on each sheet.
2. Enter Day of Week Subject is to start taking medicine. This should be the same for each sheet.
3. Under Day 1 enter the day of the week that subject is to start taking medicine. Under each subsequent Day enter the next day of the week.
4. Circle the assigned number of Famotidine tablets to take thrice daily.
5. Circle the assigned number of N-Acetyl Cysteine capsules to take thrice daily.

Instructions for Research Subject:

1. You will be assigned to take one, two or three Famotidine tablets three times a day. Please enter the time of day for the correct day for each dose you take.
2. You will take the N-Acetyl Cysteine capsules thrice a day. You will be assigned to take one, two or three capsules each time. Please enter the time of day for the correct day for each dose you take.
3. Please note that the days of each new week should correspond to the same day of the week you started on the trial which won't necessarily be a Monday or Sunday.
4. Please call the study coordinator if you have any questions. If you cannot get a hold of the study coordinator, then please call the Principal Investigator, [name]., at any time day or night at [name].

Instruction Sheet for Roth Score and 40 Step Test

Roth Score

The Roth Score has not been proven to be an effect measure of one's respiratory status and may lead to a false reassurance. It has not been previously studied in patients with a SARS-CoV-2 infection. If you feel your ability to breathe is worsening, you should seek medical attention immediately. We are asking you to perform this test daily for research purposes so that we can better understand the severity of a SARS-CoV-2 infection. It is possible that we may learn that changes in the Roth Score together with other objective measures may allow us to understand earlier predictors for severity of a SARS-CoV-2 infection.

To perform this test correctly you will need to take a deep breath followed by counting out loud from 1 to 30 in your native language, in a single breath, as rapidly as possible. You should stop your count when you reach 30 or take another breath whichever comes first. You will also need to use a physical or electronic stopwatch with a second hand and measure in seconds the time it takes between your count of 1 and the highest number you achieve. The result of the Roth score includes 2 measurements: (1) the duration of time elapsed between counting from 1 to 30 in 1 breath, or until the you take another breath; and (2) the highest number you reach in 1 breath. The first measurement is known as the "counting time" and this should be entered your Daily Diary in the row labelled "Roth Score" under the AM column. The second measurement is known as the "maximal count" and should be entered under the PM column. You only need perform this test once daily and ideally around the same time of day.

40 Step Test

The 40 Step Test should only be performed under the direct supervision of a health care provider and for the purposes of this trial will be done during your weekly virtual visit with one of the trial investigators. There is no evidence that this test is harmful; however, its safety has also not been conclusively proven. This test has not been studied previously in patients with a SARS-CoV-2 infection. This test is an exertional desaturation test and a determination will be made by the study investigator at the time of your weekly virtual visit. You will not have to perform this test if you are uncomfortable or unable to do so.

This test will only be administered if you were provided a pulse oximetry device. You will be asked to measure oxygen saturation prior to beginning this test. You will then be asked to walk 40 steps on a level surface, and you will then measure your oxygen saturation after completing your 40 step walk.

Figure of REDCap® Data Entry Forms Mapped by Event

Data Collection Instrument	Enrollment (1)	Post Enrollment (2)	COVID-19 Result - Randomize (3)	Research Labs (4)	Outpatient Follow-up (5)	Hospital Follow-up (5)	Study Completion (7)
Eligibility Assessment Case Report Form	✓						
Demographics	✓						
CURB-65 Case Report Form	✓						
International Prostate Symptoms Score Questionnaire Case Report Form	✓						✓
CAP-SYM 18 Case Report Form	✓				✓		✓
Post Enrollment Checklist	✓						
Baseline Data		✓					
CBC		✓					
BMP		✓					
Coag		✓					
Liver Panel		✓					
C Reactive Protein		✓				✓	
Pregnancy Test		✓					
EKG		✓			✓	✓	
Blood Gas		✓			✓	✓	
PSA		✓					
Starting Medications		✓					
COVID-19 Test Result and Drug Randomization Case Report Form			✓				
Investigator Assignment			✓				
Medication Log							
Trial Drug Adjustment					✓		
Daily Medication Log					✓		
Daily Diary					✓		
New Medications					✓	✓	
Research Assistant Weekly Assessment					✓		
Investigator Weekly Assessment					✓		
Blood Type				✓			
Cytokine Panel				✓			
COVID-19 NP Swab Results						✓	
Hospital Admission						✓	
Supplemental Oxygen Started or Increased						✓	
Intubation						✓	
Extubation						✓	
Supplemental Oxygen Decreased or Stopped						✓	
ICU Admission						✓	
ICU Discharge						✓	
Hospital Discharge						✓	
Completion Data							✓
Antibody Results						✓	
NCI Adverse Event Serious Adverse Event CTCAE v5					✓		

N.B. Not all forms are required and most have very few data fields but allow for multiple instances and thus were created as separate data entry forms

Table of Contents of REDCap® Data Entry Form Attachment

Eligibility Assessment CRF	Page 1
Demographics CRF	Page 4
CURB-65 CRF	Page 6
IPSS CRF	Page 7
CAP-SYM 18 CRF	Page 9
Post Enrollment Checklist CRF	Page 11
Baseline Data CRF	Page 13
CBC CRF	Page 19
BMP CRF	Page 21
Coag CRF	Page 22
Liver Panel CRF	Page 23
C Reactive Protein CRF	Page 24
Pregnancy Test CRF	Page 25
EKG CRF	Page 26
Blood Gas CRF	Page 28
PSA CRF	Page 29
Starting Medications CRF	Page 30
COVID-19 Test Result and Drug Randomization CRF	Page 31
Investigator Assignment CRF	Page 36
Trial Drug Adjustment CRF	Page 40
Daily Medication Log CRF	Page 42
Daily Diary CRF	Page 43
New Medications CRF	Page 46
Research Assistant Weekly Assessment CRF	Page 47
Investigator Weekly Assessment CRF	Page 48
Blood Type CRF	page 52
Cytokine Panel CRF	Page 53
COVID 19 NP Swab Results CRF	Page 54
Hospital Admission CRF	Page 55
Supplemental Oxygen Started or Increased CRF	Page 56
Intubation CRF	Page 57
Extubation CRF	Page 58
Supplemental Oxygen Decreased or Stopped CRF	Page 59
ICU Admission CRF	Page 60
ICU Discharge CRF	Page 61
Hospital Discharge CRF	Page 62
Completion Data CRF	Page 63
Antibody Results CRF	Page 64

Responsibilities and Delegated Tasks and Responsibilities

Responsibilities	Investigator-Sponsor	Clinical Co-Investigators	Epidemiologic and Statistician Co-Investigators	Pharmacy Co-Investigators	Consultants/ Senior Medical Mentor	Study Coordinator	Research Assistants	Data And Safety Monitoring Committee
Study design and general coordination of research	X							
Advise and Support in Study Design and Conduct of Research		X	X	X	X	X	X	X
Recruit eligible subjects	X	X			X			
Screen eligible subjects	X	X			X	X	X	
Obtain informed consent	X	X			X			
Conduct research procedures involving direct interaction with subjects	X	X			X			
Prescribe Study Drug	X	X			X			
Weekly Calls with Individual Subjects to Review Compliance with taking Assigned Study Drugs,	X	X			X	X	X	

Completing Medication Log and Daily Diary. Administer CAP SYM 18 Survey and Ensure Urine Specimen has been dropped off by Subject								
Weekly Review of Inpatients Records of Subjects who have been Hospitalized	X	X			X	X	X	
Coordinate clinical laboratory tests or support	X	X			X	X	X	
Coordinate research laboratory assays, tests, or support	X	X			X	X	X	

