Subjects will be recruited from among patients at a Prisma Health-Upstate Emergency Department (ED) at either Greenville Memorial Hospital, Greer Memorial Hospital or Baptist Easley Hospital if testing for a SARS-CoV-2 infection is performed and the potential subject will be discharged to home from the ED. Potential subjects who express a desire to be evaluated for possible enrollment on trial will have their chart screened by one of the ED Investigators to ensure they meet all inclusion criteria without any exclusion criteria. If they have not had an eGFR measured within a year of enrollment, a blood draw will be performed to measure their eGFR. Female participants who are of childbearing potential, i.e., 15 to 55 years old and have not had their uterus surgically removed (i.e., hysterectomy) or both ovaries removed surgically, will have a urine pregnancy test performed. A pregnancy test will

not be performed if they would otherwise fit the category of childbearing potential described above but are of a confirmed postmenopausal state. After enrollment and while still in the ED subjects will have a blood draw for research labs that will be collected into two tubes. One tube will be sent to the main lab where it will be held. If the subject tests positive for a SARS-CoV-2 infection, they will be randomized within 24 hours of a positive test. A CURB-65 Assessment Form will be completed by the ED Investigator research staff member and a CAP-SYM 18 survey will be administered the ED Investigator. For male subjects an IPSS survey will also be completed by the ED Investigator. All subjects who have been enrolled will be provided with a signed copy of their Informed Consent Form, a copy of their signed Research HIPPA Authorization form, 30 copies of the daily diary CRF, 4 copies of the medication log CRF, an instruction sheet for the Roth Score and 40 Step Test and 4 sterile urine specimen containers.

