DLT based on the trial rules and assuming the IRB and DSMB which will have also been notified of the DLT, have not imposed further restrictions, the PI will obtain from the Statistical Lead Investigator a new “Dynamic Randomization Lookup Table.” The old “Dynamic Randomization Lookup Table” will be removed from the REDCap® “File Repository” but an electronic copy will otherwise be maintained by the Lead Statistical Investigator. The new “Dynamic Randomization Lookup Table” will be uploaded into the file repository and the User Rights to the enrollment and randomization data entry forms in REDCap® will be restored.

After the investigator has determined the trial arm to which the subject has been randomized through the two-step process as described above, the investigator will verify that they correctly accessed the “Dynamic Randomization Lookup Table” in the form entitled, “COVID-19 Test Result and Drug Randomization Case Report Form.” The remainder of the form will be completed to include entry of the trial arm and verification that the correct prescription has been entered. The subject will be notified of the randomization and prescription entry. Whenever, a Randomization CRF is saved, the PI will receive an immediate electronic notification via REDCap® and the PI will then complete the Investigator Assignment Form in REDCap®, a copy of which can be found in the Appendix. It is through this form that the subject will be assigned to an individual Investigator and an individual Research Assistant for the remainder of their trial participation. The assigned Investigator and Research Assistant will be immediately notified electronically via REDCap®. The subject will be notified by the PI to which Investigator and Research Assistant they have been assigned. Unless the subject has declined a Vivify® electronic device, such device, the trial medication and paper copies of the medication log and daily diaries will be delivered to the subject’s home within 24 hours of randomization by a courier who will have the appropriate training and PPE. If the subject has declined a Vivify® electronic device, they will be required to pick-up their study drugs and paper copies of their forms at an Upstate Pharmacy.

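### The Medication Log cannot show the 80 mg famotidine dose: it stops at three 20 mg tablets (60 mg), and 80 mg needs four

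*Combined protocol and SAP*

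**What the plan says.** The dose levels are in Research Design and Methods, Phase I Portion: "The doses to be tested for famotidine are 20 mg thrice daily, 40 mg thrice daily, 80 mg thrice daily and no famotidine". N-acetyl cysteine (NAC) is given at 600, 1200 or 1800 mg thrice daily, which makes 12 combinations.

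The Medication Log Form in the Appendices is built on 20 mg famotidine tablets and 600 mg NAC capsules. Its famotidine header reads "Dose of Famotidine 20 mg tablets Assigned to Taken Thrice Daily: 0 1 2 3 (Research Staff to Circle". Staff are told: "Circle the assigned number of Famotidine tablets to take thrice daily". Subjects are told: "You will be assigned to take one, two or three Famotidine tablets three times a day". The matching NAC header reads "Number of N-Acetyl Cysteine Capsules Assigned to Take Thrice Daily: 1 2 3 (Research Staff to Circle".

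Under Study Procedure, each enrolled subject receives "4 copies of the medication log CRF", and paper copies also go out with the study drug by courier or at pharmacy pick-up. Under Outpatient Follow-up Data Collection Process, a research assistant enters the log's contents into REDCap each week.

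**The concern.** The form and the design disagree about the top famotidine dose. In an 80 mg arm the sheet gives staff no correct figure to circle, and its printed instruction tells the subject to expect at most three tablets.

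This matters more than an ordinary slip in an appendix, for four reasons:

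- Safety of the combination is the primary outcome, and each combination is cleared or closed on three to six subjects. With so few, one subject taking 60 mg weakens a conclusion about 80 mg.
- The error runs toward under-dosing, so it would tend to make the 80 mg level look safer than it is.
- The affected arms carry the highest famotidine exposure, 240 mg/day. The escalation experience cited in the side-effect section for famotidine stops at 160 mg/day.
- The log would not reveal the problem. Subjects enter the time of each dose, not the number of tablets, so a subject on three tablets fills in the grid exactly as one on four does.

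**Working it through.** **Inputs.** The dose levels come from the Phase I Portion. Tablet strength (20 mg), capsule strength (600 mg) and the options that can be circled come from the Medication Log Form. Three subjects per arm initially, with a range of zero to six, come from Study Procedure.

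**Step 1: dose per administration = number of units × unit strength.**

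| Drug | Planned levels (mg) | Units needed | Units on the form | Dose the form can show (mg) |
|---|---|---|---|---|
| Famotidine, 20 mg | 0, 20, 40, 80 | 0, 1, 2, 4 | 0, 1, 2, 3 | 0, 20, 40, 60 |
| NAC, 600 mg | 600, 1200, 1800 | 1, 2, 3 | 1, 2, 3 | 600, 1200, 1800 |

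The NAC line reproduces all three planned levels, so the error is confined to famotidine. There the value 4 is missing and the value 3 matches nothing in the design.

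**Step 2: can another reading rescue the form?**

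- The figures 0 to 3 are not dose-level codes, because both sets of instructions call them tablets.
- No other tablet strength explains it. The grid row also specifies 20 mg, and no other strength appears in the documents.
- Damage in text extraction is unlikely, because the header and the subject sentence are both intact and agree with each other.
- A later dose reduction could explain a 3, but it would not supply the missing 4.

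**Step 3: scope.** 4 famotidine levels × 3 NAC levels = 12 combinations, of which 1 × 3 = 3 contain 80 mg. Subjects in those arms during dose escalation: 3 × 3 = 9 initially, with a range of 3 × 0 = 0 to 3 × 6 = 18. The later adaptive phase could add more, and the documents give no figure for that.

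**Step 4: worst case, assuming that a subject follows the sheet rather than the prescription.**

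- Per day: 3 × 60 = 180 mg against 3 × 80 = 240 mg. The shortfall is 60 mg, and 1 − 180/240 = 25%.
- If it is caught at the first weekly contact, assumed to be day 7 at the latest: 7 × 3 = 21 doses × 20 mg = at most 420 mg. Day 7 is also the minimum treatment time, so the contact could come only at the end of a minimum course.
- If it is never caught across four weekly sheets: 28 days × 60 mg = at most 1680 mg. Four sheets is a printing minimum, not a fixed treatment length, so this is an outer bound for a subject who uses all four.

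**The case against.** The strongest reply is that the log does not order the dose. Staff circle the figure. In an 80 mg arm they would find no 4, and would have to circle 3 against a known assignment, leave the line blank, or write in a 4. The randomization form holds the assigned arm and requires "verification that the correct prescription has been entered", and the subject is told of both. A research assistant and an investigator each make contact at least weekly, and the subject can telephone the coordinator. The assigned dose is therefore not lost, and the number actually under-dosed may be zero. No prescription or label is visible, so a conflict between the sheet and the prescription is inferred from the design levels rather than seen. The grid's failure to count tablets is common to all arms. The subject instruction's omission of zero tablets is trivial, since the header offers 0. Nothing here alters a dose level, a toxicity rule or an analysis.

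Most of this stands as a limit on the consequence. It shows that under-dosing is possible rather than expected, and that the milligram shortfalls are conditional bounds. None of it corrects the sheet. The logs in the enrollment pack may also be handed over before the test result and the arm are known. A subject could then hold a sheet whose only statement of dose is the printed range of one to three tablets.

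**Conclusion.** The inconsistency is certain. As written, the form's maximum is 60 mg per dose against the 80 mg assigned in 3 of 12 combinations, and nothing in the documents reconciles the two. It should be fixed, because the sheet is a working form held by subjects who dose themselves in a dose-finding trial.

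The consequence is conditional. The 25% shortfall, and the bounds of 420 mg and 1680 mg, apply only if the sheet overrides the verified prescription. The figure of 9 subjects (0 to 18) counts those who would hold such a sheet during escalation, not those who would be under-dosed. The REDCap form attachment is not available, so whether the electronic forms carry the same list is unknown, and the conclusion does not depend on it.

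**What to change.** Before any 80 mg arm opens:

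1. Change the famotidine options on the Medication Log Form to 0, 1, 2, 4, and change the subject instruction to none, one, two or four tablets. If 60 mg was intended, correct the famotidine levels in the Phase I Portion instead.
2. Replace the form on every route by which subjects receive it: the enrollment pack, the courier delivery and the pharmacy pick-up.
3. Check the Randomization, Daily Medication Log and Trial Drug Adjustment forms in REDCap for the same 0-to-3 list.

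The zone order leaves time for this. Zone 1 combines the lowest doses, and of zone 2 the protocol says: "The second zone has the combination of the lowest dose of each drug with the middle dose of each drug". By that description, neither includes 80 mg.

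The cost is two lines on one form, or one protocol sentence, plus a check of three electronic forms. No new data collection is needed and the sample size does not change.
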